3. INVESTIGATIONAL PLAN

3.1 Trial Design

This multicenter trial consists of a randomized, placebo-controlled, double-blind phase followed by an open-label extension (OLE) phase.

Blinded Phase:

The blinded phase of the trial is a randomized, double-blind, parallel-group, 16-week comparison of two doses of GWP42003-P vs. placebo. Patients will complete a 1-week screening period and a 4-week baseline period before they are randomized to receive either 25 mg/kg/day GWP42003-P, 50 mg/kg/day GWP42003 P or placebo. Randomization will be stratified by age according to the following ranges: 1–6, 7–11, 12–17 years and 18–65 years. Patients will begin a 4-week dose escalation period, titrating up to their assigned dose, before continuing on a stable dose of blinded Investigational Medicinal Product (IMP) for 12 weeks.

Dose escalation for each patient is subject to the investigator's assessment of safety and tolerability. If a dose becomes poorly tolerated, the investigator may consider temporarily or permanently reducing the dose for the remainder of the trial.

Following completion of the blinded phase, patients will be invited to continue to receive GWP42003-P in an OLE.

Those patients opting not to enter the OLE will complete a 10-day taper period (down-titrating 10% per day for 10 days).

Open-label Extension Transition:

In order to maintain consistent exposure to IMP and maintain the integrity of the blind, patients will enter a 2-week blinded transition to the OLE. OLE IMP will be titrated up to 25 mg/kg/day whilst blinded IMP is simultaneously tapered down to zero. All patients will complete the transition and enter the OLE taking 25 mg/kg/day GWP42003-P:

- Patients from the placebo arm will titrate up to 25 mg/kg/day GWP42003-P.
- Patients from the 25 mg/kg/day GWP42003-P arm will continue to take 25 mg/kg/day GWP42003-P.
- Patients from the 50 mg/kg/day GWP42003-P arm will taper down (10% per day) to 25 mg/kg/day GWP42003-P.

Open-label Extension:

The OLE consists of a 3-week titration period followed by a maintenance period and a 10-day taper period. The initial OLE period will last for a maximum of 1 year.

Following titration according to the titration schedule, patients will continue with their optimal GWP42003-P dose. However, investigators may decrease the dose if a patient experiences intolerance, or increase the dose to a maximum of 50 mg/kg/day if required for better seizure control, until the optimal dose is found.

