5.6 Safety Evaluation

5.6.1 Exposure to IMP

Blinded Phase:

Patients are required to take IMP twice daily (morning and evening). The first dose will be taken in the clinic on Day 1. The date of final dose in the treatment phase will be recorded on the CRF. The date of final dose, for patients who enter the taper period, will be recorded on the CRF at the end of taper visit.

The total number of dosing days in the treatment phase will be calculated as:

$$(\text{Date of last dose in the treatment phase} - \text{Date of Day 1}) + 1$$

The date of last dose in the treatment phase will be obtained from the CRF at the end of treatment visit.

Any missed doses during treatment should be recorded on the 'IMP Missed Doses Log' CRF page. The number of days with any missed doses and the number of days where trial medication was not taken in the AM nor PM will be summarized based on data in the treatment phase (Day 1 to end of treatment visit).

In addition, the number of days in which trial medication was taken at least once (AM or PM) will be summarized and calculated as:

$$\text{Total number of dosing days} - \text{the number of days where trial medication was not taken in the AM nor PM}$$

The number of days in which trial medication was taken both AM and PM will be summarized and calculated as:

$$\text{Total number of dosing days} - \text{the number of days with any missed doses}$$

The above summaries will be presented for all patients and repeated for patients who completed the treatment phase.

In addition, the expected daily volume of IMP to be administered during the treatment phase, once a patient has titrated to target dose, will be summarized by treatment.

The expected daily volume of IMP will be calculated as:

$$2 \times [\text{Weight (kg) at Day 1} \div 8 \text{ and rounded to the nearest } 0.1]$$

for patients randomized to the 25 mg/kg/day dose level and:

$$2 \times [\text{Weight (kg) at Day 1} \div 4 \text{ and rounded to the nearest } 0.1]$$

for patients randomized to the 50 mg/kg/day dose level.

Finally, IMP compliance will be summarized by treatment and calculated as:

$$100 \times (\text{Number of days IMP taken at least once} + \text{number of days IMP taken both AM and PM}) \div (2 \times \text{day of completion or withdrawal during the treatment period})$$

Open-label Extension:

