5.7.2 Pharmacokinetics of CBD and its Major Metabolites

Samples for PK analysis are taken on Visit 3 (first dose, Day 1) and Visit 10 (last maintenance dose of the blinded phase, Day 113) for patients weighing more than 20 kg. For patients recruited under Protocol Version 2, PK samples were taken at the following time-points:

- Prior to administration of IMP, ≤ 0.0 hours pre-dose on Visit 3 or C_{trough} at steady state (Visit 10).
- ≥ 4.0 hours to ≤ 5.0 hours.
- ≥ 6.0 hours to ≤ 7.0 hours.
- ≥ 8.0 hours to ≤ 10.0 hours, for patients 18 years or older.

Patients recruited under Protocol Version 3 onwards, PK samples were taken at the following time-points:

- Prior to administration of IMP, ≤ 0.0 hours pre-dose on Visit 3 or C_{trough} at steady state (Visit 10).
- ≥ 2.0 hours to ≤ 3.0 hours.
- ≥ 4.0 hours to ≤ 6.0 hours.
- ≥ 8.0 hours to ≤ 10.0 hours, for patients 18 years or older.

The nominal mid-point time of 0, 2.5, 4.5, 5, 6.5 and 9 hours will be used for summaries of plasma concentrations. Plasma concentrations and PK parameters will be summarized showing the number of non-missing values (n), arithmetic mean, standard deviation, coefficient of variation (%), median, minimum and maximum. Where samples are reported as BLQ, a value of zero will be used in the summaries. Summary statistics will be presented to 3 significant figures.

Where data allow, the PK parameter AUC_{0-t} , will be derived at each visit by the PK vendor. A dose-normalized AUC_{0-t} will be calculated as AUC_{0-t} divided by the randomized dose per administration (12.5 or 25 mg/kg). This will include Visit 3, for consistency, where the first dose of IMP will be 2.5 mg/kg.

Plasma concentrations of CBD and its major metabolites 7-hydroxy-CBD (7-OH-CBD) and 7-carboxy-CBD (7-COOH-CBD) will be summarized by nominal mid-point time, visit and GWP42003-P arm. In addition, a dot plot of plasma concentrations for each patient, by nominal mid-point time will be created for each visit and GWP42003-P arm. The arithmetic mean will be highlighted on the plot. Additionally, a line plot of the arithmetic mean plasma concentration will be created with standard error bars by nominal mid-point time for each visit and GWP42003-P arm. These plots will be presented both a linear and semi-logarithmic scale for plasma concentration.

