AUC_{0-t} and dose normalized AUC_{0-t} , for CBD and its major metabolites 7-OH-CBD and 7-COOH-CBD, will be summarized by visit and GWP42003-P arm. In addition, the ratio of 7-OH-CBD AUC_{0-t} to CBD AUC_{0-t} and the ratio of 7-COOH-CBD AUC_{0-t} to CBD AUC_{0-t} will be summarized. Box plots of AUC_{0-t} will be produced comparing visit on the x-axis, by parent and metabolite, and GWP42003-P arm. This will be repeated with parent and metabolite on the x-axis, by visit and GWP42003-P arm. Summaries and plots of AUC_{0-t} will be repeated by stratified age group.

Plasma concentration and AUC_{0-t} summaries may exclude individual time-points or visits for patients deemed to meet certain criteria that could affect exposure. These criteria include:

- Patients vomiting on or 1 day prior to the PK visit.
- Missed doses prior to the PK visit.
- IMP dose reduction.
- Cases of severe diarrhoea.
- Use of disallowed concomitant medication.

All exclusion will be detailed in a separate document finalized prior to unblinding. All data will be listed with data excluded from summaries flagged along with the reason for exclusion.

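### Dose-normalized AUC at Visit 3 is divided by the randomized dose instead of the 2.5 mg/kg first dose that the SAP states, so the values are 5-fold and 10-fold too small

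*SAP*

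**What the plan says.** SAP Section 5.7.2 sets the sampling days: "Samples for PK analysis are taken on Visit 3 (first dose, Day 1) and Visit 10 (last maintenance dose of the blinded phase, Day 113"). At each of these visits it derives AUC0-t and a dose-normalized version, in which AUC0-t is "divided by the randomized dose per administration (12.5 or 25 mg/kg"). The next sentence extends the rule to the first-dose visit: "This will include Visit 3, for consistency, where the first dose of IMP will be 2.5 mg/kg".

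Three other statements bear on this:

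- Section 3.1 has patients "randomized to receive either 25 mg/kg/day GWP42003-P, 50 mg/kg/day GWP42003 P or placebo".
- Section 3.1 also shows that the assigned dose is not reached on Day 1: "Patients will begin a 4-week dose escalation period, titrating up to their assigned dose".
- Section 5.6.1 gives the dosing frequency: "Patients are required to take IMP twice daily (morning and evening").

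For reporting, Section 5.7.2 tabulates the raw and the normalized AUC0-t of the parent drug and its two metabolites, separately for each visit and active arm. The matching output in the SAP's Appendix 6 is Table 14.8.2.1, the summary of PK parameters.

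**The concern.** Dose normalization expresses exposure per unit of dose taken. It works only if the divisor is the dose that produced the measured AUC. At Visit 10 the randomized dose per administration is that dose for any patient who reached and kept it. At Visit 3 it is not, because titration has only begun and the SAP gives the first dose as 2.5 mg/kg. The Visit 3 value is then raw AUC divided by an arm-specific constant unrelated to what the patient took.

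Two comparisons in the table suffer. Between arms at Visit 3, the two divisors differ by a factor of two although one first dose is stated, so a gap appears that the kinetics did not produce. Between visits within an arm, the variable carries a dose-normalized label but leaves the whole effect of titration in place. A reader could take the first for less-than-proportional exposure and the second for accumulation.

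**Working it through.** Inputs, all from the SAP:

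- Daily doses: 25 and 50 mg/kg/day (Section 3.1).
- Two administrations a day (Section 5.6.1).
- Stated divisors: 12.5 and 25 mg/kg (Section 5.7.2).
- Stated first dose: 2.5 mg/kg, given once without separating the arms (Section 5.7.2).

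**Step 1: reproduce the plan's divisors.** Dose per administration = daily dose ÷ 2. So 25 ÷ 2 = 12.5 mg/kg and 50 ÷ 2 = 25 mg/kg. Both agree with the SAP.

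**Step 2: understatement at Visit 3.** Factor = divisor used ÷ dose given.

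- 25 mg/kg/day arm: 12.5 ÷ 2.5 = 5
- 50 mg/kg/day arm: 25 ÷ 2.5 = 10

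**Step 3: between-arm effect at Visit 3.** For the same AUC in both arms, the ratio of normalized values (25 arm to 50 arm) = 25 ÷ 12.5 = 2. It should be 1. With an assumed AUC of 100 in each arm, in arbitrary units:

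| | 25 mg/kg/day arm | 50 mg/kg/day arm | Ratio |
|---|---|---|---|
| SAP rule | 100 ÷ 12.5 = 8.0 | 100 ÷ 25 = 4.0 | 2.0 |
| Divided by 2.5 | 40.0 | 40.0 | 1.0 |

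**Step 4: between-visit effect within an arm.** Let A3 and A10 be a patient's raw AUC0-t at Visits 3 and 10, and D the randomized dose per administration, with the patient on D at Visit 10.

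- SAP rule: (A10 ÷ D) ÷ (A3 ÷ D) = A10 ÷ A3, the raw ratio.
- Proper normalization: (A10 ÷ D) ÷ (A3 ÷ 2.5) = (A10 ÷ A3) × (2.5 ÷ D).
- SAP ratio over proper ratio: D ÷ 2.5 = 5 or 10.

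This last factor needs no assumption about the kinetics. As an illustration only, with dose-linear kinetics and no accumulation the proper ratio is 1, and the SAP rule would show 5 and 10.

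**Step 5: sensitivity to the reading of 2.5 mg/kg.** The SAP calls it the first dose, so it is taken as a single administration. If it were a daily amount, each administration would be 1.25 mg/kg and the factors in Step 2 would be 12.5 ÷ 1.25 = 10 and 25 ÷ 1.25 = 20. The 2-fold arm effect is the same for any first dose common to both arms.

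**The case against.** The strongest defence is that nothing is hidden. The divisor, the true first dose and the decision to keep one divisor stand in adjacent sentences, and a reader can undo the rule by multiplying Visit 3 values by 5 or 10. That holds, and it is one reason the point is minor. Disclosure still does not make the quantity dose-normalized, and someone reading the table without Section 5.7.2 will not know to correct it.

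One could also read the sentence as meaning that Visit 3 is divided by 2.5. That is weak. Its opening words refer back to the randomized-dose rule, and the appeal to consistency makes sense only if that divisor is kept. If 2.5 was meant, the sentence needs rewording anyway.

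The limited reach stands in full. Section 3.3.3 names plasma concentrations and AUC0-t as the PK endpoints and does not mention a dose-normalized AUC. No test of it is planned, and the objective of describing single- and multiple-dose PK can be met from the un-normalized results.

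Three stronger readings might be inferred, and the SAP does not support them:

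- *That the rule invents a rise from Visit 3 to Visit 10.* The ratio equals the raw AUC ratio, so the rise is real exposure growth that includes titration. The fault is that the dose effect is not removed.
- *That comparing visits and arms is the sole use of the variable, so that it is worthless.* The SAP states no purpose for it, and Visit 10 values are sound for patients on their randomized dose.
- *That age-group summaries are confounded by sampling length, because the 8 to 10 hour sample is restricted: "hours, for patients 18 years or older".* Section 3.3.3 declares that AUC0-t runs to the last measurable time-point. Within a protocol version only the adult stratum has the extra sample. Any numerical factor would need an assumed concentration profile. The matter is also unrelated to the divisor.

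**Conclusion.** The concern holds for the Visit 3 divisor, and its severity is minor. As written, Visit 3 dose-normalized AUC0-t of CBD and both metabolites is 5-fold too small in the 25 mg/kg/day arm and 10-fold too small in the 50 mg/kg/day arm. The Visit 10 to Visit 3 ratio is 5 or 10 times the properly normalized ratio.

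The 2-fold between-arm artefact rests on one assumption: that both active arms receive the same first dose. The single unqualified value in Section 5.7.2 implies this, but the titration schedule is in the protocol, which is not at hand. The factors 5 and 10 also take 2.5 mg/kg as one administration.

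Only the Visit 3 dose-normalized AUC rows of Table 14.8.2.1 are affected, and these are descriptive and exploratory. Raw AUC0-t, its box plots, the metabolite-to-parent ratios and all efficacy analyses are untouched.

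**What to change.** In Section 5.7.2, define dose-normalized AUC0-t as AUC0-t divided by the dose recorded as administered at that visit, and delete the sentence that extends the randomized-dose divisor to Visit 3. For Visit 3 the SAP states that dose as 2.5 mg/kg. Omitting dose-normalized AUC at Visit 3 would serve equally well.

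At Visit 10, apply the same definition to any dose-reduced patient who stays in the summary. Section 3.1 allows dose reductions, and Section 5.7.2 says only that such patients may be excluded, so some could otherwise be divided by a dose they were not taking.

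The cost is a wording change, a new divisor and a rerun of the affected rows of one table. It needs no new data and no new AUC derivation. The SAP addendum (Section 2.4.1) already plans to derive each active-arm patient's dose at the end of the blinded treatment period, which could supply the Visit 10 divisor after conversion from a daily to a per-administration dose. The change concerns the analysis divisor only and has no bearing on dosing.

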3.3.3 Exploratory Endpoints (Double-blind and Open-label Extension)

Antiepileptic Efficacy Measures:

- Change in composite focal seizure score (frequency \times severity).
- Change in number of seizures by subtype.
- Change in use of rescue medication.
- Change in the number of episodes of status epilepticus (convulsive and non-convulsive).
- Changes in duration of seizure subtypes as assessed by the Subject Global Impression of Change in Seizure Duration (SGIC-SD) or the Caregiver Global Impression of Change in Seizure Duration (CGIC-SD).

TAND:

Cognitive and Behavioral Function:

- Changes in Vineland Adaptive Behavior Scales, Second Edition (Vineland-II).

- Changes in Wechsler Scales (pre-school, primary, children, adult).
- Changes in Achenbach Child Behavior Checklists (CBCL) and Adult Behavior Checklist (ABCL).

Autistic Features:

Change in Social Communication Questionnaire (SCQ) score.

PK (Double-blind only):

- The plasma concentrations will be summarized by time window for CBD and its major metabolites following single and multiple doses of GWP42003-P. Where data allows, the area under the plasma concentration curve (AUC_{0-t}) from time zero to the last measurable time-point will be calculated.
- Plasma concentrations of concomitant AEDs before and after treatment with GWP42003-P, where available.

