Figure 14.2.3.3.2.5	Box Plot of AUC _{0-t} by Parent and Metabolites for Visit 10 (25 mg/kg/day), Age 18 to 65 Years	Safety Analysis Set
Figure 14.2.3.4.1.1	Box Plot of AUC _{0-t} by Parent and Metabolites for Visit 3 (50 mg/kg/day)	Safety Analysis Set
Figure 14.2.3.4.1.2	Box Plot of AUC _{0-t} by Parent and Metabolites for Visit 3 (50 mg/kg/day), Age 1 to 6 Years	Safety Analysis Set
Figure 14.2.3.4.1.3	Box Plot of AUC _{0-t} by Parent and Metabolites for Visit 3 (50 mg/kg/day), Age 7 to 11 Years	Safety Analysis Set
Figure 14.2.3.4.1.4	Box Plot of AUC _{0-t} by Parent and Metabolites for Visit 3 (50 mg/kg/day), Age 12 to 17 Years	Safety Analysis Set
Figure 14.2.3.4.1.5	Box Plot of AUC _{0-t} by Parent and Metabolites for Visit 3 (50 mg/kg/day), Age 18 to 65 Years	Safety Analysis Set
Figure 14.2.3.4.2.1	Box Plot of AUC _{0-t} by Parent and Metabolites for Visit 10 (25 mg/kg/day)	Safety Analysis Set
Figure 14.2.3.4.2.2	Box Plot of AUC _{0-t} by Parent and Metabolites for Visit 10 (25 mg/kg/day), Age 1 to 6 Years	Safety Analysis Set
Figure 14.2.3.4.2.3	Box Plot of AUC _{0-t} by Parent and Metabolites for Visit 10 (25 mg/kg/day), Age 7 to 11 Years	Safety Analysis Set
Figure 14.2.3.4.2.4	Box Plot of AUC _{0-t} by Parent and Metabolites for Visit 10 (25 mg/kg/day), Age 12 to 17 Years	Safety Analysis Set
Figure 14.2.3.4.2.5	Box Plot of AUC _{0-t} by Parent and Metabolites for Visit 10 (25 mg/kg/day), Age 18 to 65 Years	Safety Analysis Set

Table 22 List of OLE Phase Figures

Figure Number	Title	Analysis Set
OLE Figure 9.1.1	Percentage Change in TSC-associated Seizure Frequency Over Time	OLE Safety Analysis Set
OLE Figure 9.1.2	Percentage Change in TSC-associated Seizure Frequency Over Time (LOCF)	OLE Safety Analysis Set

OLE Figure 9.1.3	Percentage Change in TSC-associated Seizure Frequency Over Time (Patients with Data in OLE Week 37 to 48)	OLE Safety Analysis Set
OLE Figure 9.2.1	Percentage Change in Total Seizure Frequency Over Time	OLE Safety Analysis Set
OLE Figure 9.2.2	Percentage Change in Total Seizure Frequency Over Time (LOCF)	OLE Safety Analysis Set
OLE Figure 9.2.3	Percentage Change in Total Seizure Frequency Over Time (Patients with Data in OLE Week 37 to 48)	OLE Safety Analysis Set

GW Research Ltd.

Trial Code: GWEP1521

**A DOUBLE-BLIND, RANDOMIZED, PLACEBO-CONTROLLED
STUDY TO INVESTIGATE THE EFFICACY AND SAFETY OF
CANNABIDIOL (GWP42003-P, CBD) AS ADD-ON THERAPY IN
PATIENTS WITH TUBEROUS SCLEROSIS COMPLEX WHO

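### AUC0-t stops at about 9 h in adults but at about 5 h or 6.5 h in under-18s, yet it is pooled and repeated by age group with no common interval

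*SAP*

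**What the plan says.** SAP section 3.3.3 defines the area as running "from time zero to the last measurable time-point will be calculated", where data allow. Section 5.7.2 leaves the derivation to the PK vendor and gives two sampling schedules:

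- Both schedules: a pre-dose sample, and a final sample at "≥ 8.0 hours to ≤ 10.0 hours, for patients 18 years or older".
- Protocol Version 2: samples at 4 to 5 h and then "≥ 6.0 hours to ≤ 7.0 hours". The latter is the last sample for patients under 18.
- Protocol Version 3 onwards: samples at 2 to 3 h and then "≥ 4.0 hours to ≤ 6.0 hours". The latter is the last sample for patients under 18.

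For concentrations, "The nominal mid-point time of 0, 2.5, 4.5, 5, 6.5 and 9 hours will be used for summaries of plasma concentrations". Section 5.7.2 then summarizes AUC0-t, its dose-normalized form and the metabolite-to-parent AUC ratios by visit and active arm, without separating ages or protocol versions. It adds: "Summaries and plots of AUC_{0-t} will be repeated by stratified age group". Appendix 6 lists the PK parameter and ratio tables both overall and by age group, and a box plot for each of the four age strata. The SAP fixes no common end time, no split by protocol version, and no note that the oldest stratum covers a longer interval.

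**The concern.** An area under a curve depends on how long the curve is followed. Here the follow-up time is set by age: the cut-off for the late sample (18 years) is also the lower limit of the 18–65 stratum. Sampling length is therefore completely confounded with membership of that stratum. A reader who sets the adult table beside the paediatric ones would see higher adult exposure even if every concentration were the same.

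Three further outputs are touched. The overall summaries mix areas over about 5, 6.5 and 9 h, which adds spread unrelated to exposure. Metabolite-to-parent ratios share one end time within a patient, but after a first dose a metabolite may still be accumulating, so the ratio can rise with sampling length. The mean concentration line plots join points from different patients: 2.5 and 5 h come only from Version 3 onwards, 4.5 and 6.5 h only from Version 2, and 9 h only from adults.

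**Working it through.** **Inputs from the SAP.** Window mid-points, (lower + upper)/2: 2–3 h gives 2.5; 4–5 h gives 4.5; 4–6 h gives 5; 6–7 h gives 6.5; 8–10 h gives 9. These reproduce the nominal times in section 5.7.2.

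**Assumed.** The SAP gives no concentration profile. Adult and child are given the same curve, so any AUC ratio other than 1 comes from the schedule. The integration rule is also not stated; the linear trapezoid at nominal times is used.

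**Step 1, flat curve.** AUC is proportional to the end time.

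- Version 3 onwards, adult/child: 9/5 = 1.80. At the window limits: 8/6 = 1.33 to 10/4 = 2.50.
- Version 2, adult/child: 9/6.5 = 1.38. At the window limits: 8/7 = 1.14 to 10/6 = 1.67.
- Version 2 child/Version 3 child: 6.5/5 = 1.30.

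**Step 2, one worked single-dose curve.** C(t) = exp(−0.1t) − exp(−0.5t), up to a constant that cancels. This gives C(2.5) = 0.4923, C(4.5) = 0.5322, C(5) = 0.5244, C(6.5) = 0.4833, C(9) = 0.3955.

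- Version 3 child: 2.5 × 0.4923/2 + 2.5 × (0.4923 + 0.5244)/2 = 1.886.
- Version 3 adult: 1.886 + 4 × (0.5244 + 0.3955)/2 = 3.726. Ratio 1.98.
- Version 2 child: 4.5 × 0.5322/2 + 2 × (0.5322 + 0.4833)/2 = 2.213.
- Version 2 adult: 2.213 + 2.5 × (0.4833 + 0.3955)/2 = 3.311. Ratio 1.50.

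**Step 3, ranges of adult/child ratio.** One-compartment oral model; Visit 3 as a single dose, Visit 10 as steady state with a 12 h interval. The wide grid is Tmax 2–6 h and half-life 2–48 h. The narrow grid is absorption rate 0.3–0.6/h and elimination rate 0.1–0.25/h.

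| Schedule | Visit | Wide grid | Narrow grid |
|---|---|---|---|
| Version 3 onwards | 3 | 1.47–2.22 (median 1.98) | 1.63–2.16 |
| Version 3 onwards | 10 | 1.46–1.81 (median 1.76) | 1.58–1.80 |
| Version 2 | 3 | 1.27–1.59 (median 1.53) | 1.34–1.56 |
| Version 2 | 10 | 1.25–1.39 (median 1.38) | 1.31–1.39 |

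Linear-up/log-down integration gives nearly the same figures.

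**Step 4, metabolite-to-parent ratio at Visit 3.** Narrow grid, metabolite formed from the parent, metabolite elimination assumed at 0.02–0.5/h: the adult/child ratio of ratios within Version 3 onwards is 1.25–1.87 for identical kinetics.

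**Step 5, does a common interval cure it?** Within one version, yes. Cutting everyone at 5 h on the Version 3 grid, or at 6.5 h on the Version 2 grid, gives an adult/child ratio of 1.00.

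Across versions, no. Version 2 has no sample between pre-dose and 4 h, so its AUC0-4h is a single straight line from pre-dose. For the Step 2 curve:

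- Version 3: interpolated C(4) = 0.4923 + (1.5/2.5) × (0.5244 − 0.4923) = 0.5116. AUC0-4h = 2.5 × 0.4923/2 + 1.5 × (0.4923 + 0.5116)/2 = 1.368.
- Version 2: interpolated C(4) = 0.5322 × 4/4.5 = 0.4731. AUC0-4h = 4 × 0.4731/2 = 0.946.
- Version 2/Version 3 = 0.69 for the same curve.

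Over the narrow grid this ratio is 0.56–0.77 at Visit 3 and 0.63–0.91 at Visit 10.

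**The case against.** The strongest reply is that little depends on these outputs. PK is an exploratory objective, concerned with describing CBD and its metabolites after single and multiple doses. Comparing exposure across ages is not a stated objective. No age test is planned, and the box plots have visit or analyte on the axis, with a separate figure per age group. Three of the four strata share one schedule within each protocol version. Splitting by age also separates the 9 h patients from the rest. Randomization is stratified by age, so the arms do not differ systematically in sampling length.

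All of this stands, and it limits the consequence. It does not remove the defect: the overall tables still pool unequal intervals, and by-age tables of one parameter under one label invite the comparison they cannot support.

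A reader might infer that adults will show 1.6 to 2.2 times the AUC of children in general. The documents do not support that. A factor in that range belongs to children on the Version 3 schedule, and its upper part only to the single-dose visit. Against Version 2 children the factor is smaller, and every factor other than a ratio of end times rests on a curve shape the SAP does not give. A reader might also infer that the results would mislead a judgement on whether dosing by weight suits all ages. The SAP assigns them no such use.

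**Conclusion.** The point holds. Followed exactly, the plan gives the 18–65 stratum a larger AUC0-t than under-18s with identical concentrations: about 1.5 to 2.2 times within Version 3 onwards (1.8 if flat) and about 1.25 to 1.6 times within Version 2 (1.4 if flat). The differing end times are on the face of the SAP. The ranges assume one-compartment oral kinetics, the same curve at all ages, and samples at the nominal times. What is affected is the reading of the by-age summaries, the spread and meaning of the overall ones, and metabolite-to-parent ratios at Visit 3 if the metabolite is still accumulating. Dose-arm comparisons are not systematically biased, and no efficacy conclusion is touched. The change is worth making because it is cheap.

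**What to change.** In section 5.7.2, base the overall, by-age and metabolite-to-parent summaries on a partial AUC over one common interval within each protocol version, interpolated at actual sampling times: to about 4–5 h for Version 3 onwards and to about 6–6.5 h for Version 2. The lower limits, 4 h and 6 h, are reached by every patient whose last scheduled sample before the adult-only one falls within its window and is measurable. Present the results separately by protocol version. A single interval such as AUC0-4h pooled over versions should be avoided, for the reason in Step 5 of the working. Report AUC to about 9 h for adults only, labelled as such. Draw mean concentration curves separately by protocol version and by under 18 versus 18 and over.

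The cost is a re-derivation by the PK vendor from existing concentrations, plus revised wording and table shells. Less of the dosing interval is covered, and the groups are smaller.

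A separate clerical correction: in Appendix 6, Figures 14.2.3.4.2.1 to 14.2.3.4.2.5 are titled "by Parent and Metabolites for Visit 10 (25 mg/kg/day"), repeating Figures 14.2.3.3.2.1 to 14.2.3.3.2.5. They follow the 50 mg/kg/day Visit 3 figures, and no Visit 10 plot of this type is listed for that arm.
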